2.3 Interventions

The study will assess acceptance and interaction of patients and clinicians to implementation of a smart device to monitor weight-bearing during the rehabilitation phase following surgery of an unstable ankle fracture. Postoperative rehabilitation will be standardised for the initial 12-week rehabilitation period for all included patients, in accordance with current clinical practice. The patients' weight-bearing and activity will be recorded with the Magnes device.

This study does not examine the effectiveness of surgical or rehabilitation strategies. However, clinical outcomes will be recorded to allow exploration of the correlation between weight-bearing activities, clinical progress and adverse events. The future application of the Magnes device would allow to detect aberrant movement patterns early, hence avoiding complications following ankle fracture fixation.

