3.1 Magnes Device specific Outcome Measures

The Magnes Device uses a lithium polymer battery and can collect approximately 16 hours of data on a single charge and can store data equivalent to 25 days of use. It can record gait parameters (i.e. step velocity, step length, swing time, step time, stance time) and the loading behaviour (i.e. peak load, average load, load duration, steps/day). Force is recorded in Newtons (N). The boot communicates to an iPhone/iPad application via Bluetooth low energy to start/stop data collection. The data are transferred to the smartphone/iPad via WLAN.

Aim 1:

The patient acceptability and feasibility of using this device in the Aircast boot during rehabilitation (week 1 to approximately week 6)

Feasibility

- Percentage of weight-bearing per week
- The correlation between instructed amount of weight-bearing and actual weight-bearing, in both intensity and total time.

Acceptability

- Ability to maintain charge in device
- Adverse events recorded relevant to the use of the Magnes smart device
- Open-ended /a semi-structured phone interview after Assessment 3 (12 weeks postoperatively) will be conducted and analysed to gain insight in the acceptability of using the Magnes smart device in the Aircast boot during postoperative rehabilitation. Every second participant will be selected to receive a phone call (participants 2, 4, 6, 8, 10, 12).

Aim 2:

The patient acceptability and feasibility of using the Magnes NUSHU during rehabilitation (from approximately week 6 to week 12)

Feasibility

- Time to fully weight-bear
- Percentage of weight-bearing per week
- The correlation between instructed amount of weight-bearing and actual weight-bearing

Acceptability

- Ability to maintain charge in device
- Adverse events recorded in regard to the Magnes smart device
- Semi-structured phone interview after Assessment 3 (12 weeks postoperatively) will be conducted and analysed to gain insight in the acceptability of using the Magnes smart device in NUSHU during postoperative rehabilitation.

Aim 3:

The clinician acceptability and usability of the data recorded by both devices (Magnes and NUSHU), for clinical decision-making

Feasibility

- Ability to upload data consistently during the exhibition phase

Acceptability

- A semi-structured interview will be conducted and analysed to gain insight in the usefulness of using data collected with the smart devices to inform clinical decision making.

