APPENDIX 1: Rehabilitation protocol

Ankle Fracture - Post operative Physiotherapy

The following is a guide only, please check for any changes or variances as indicated by your surgeon's post-operative plan.

(Excludes tibial plafond fractures and large posterior malleolar fractures)

0 to 2 weeks Gentle walking and elevation PWB

- Physiotherapy review post operatively for crutches
- Apply air-cast boot in theatre after surgery – No inflation
- **PWB (partial weight bear)** in air-cast boot with crutches is ok
You may opt to NWB (non-weight bear) due to pain, this is ok too.
After 3-5 days start to try and take some weight (<50% of your weight) on your

foot with the boot

- Keep boot on at all times - leave on 24/7 but check your skin underneath by undoing daily to view your skin by removing the front panel
- Rest and elevate to allow for wound healing – aim to keep your leg elevated 23hrs/day
 - When sitting elevate your leg on a foot stool, chair or up on sofa
 - When lying down, you can elevate your leg on a single pillow
 - Don't walk too much, aim for essential walking within your home in the first week
- Do not get dressings wet – cover your lower leg in a cast bag for showering
- Leave dressings intact for 10-14 days - until the '2 week' follow up
- Around 2 weeks you will have dressing removed and wound reviewed by a doctor
- A tubi-grip will be applied and the air-cast boot re-applied
- Teach application of air-cast boot – **but not to inflate for first 2weeks** and until dressing removed

Video demo: <https://www.youtube.com/watch?v=XnBm68oTDOw>

Crutches PWB = Partial Weight Bear

= <50% of your body weight

Boot on at all times

- Aim for ankle in neutral (90°)
- Can be refitted if needed to ensure heel down
- Or to check skin condition daily.

[figure not shown]
Walking with crutches:

- Crutches in front first, boot foot next taking **Partial weight** as pain allows (**up to 50% of your body weight**), good foot follows stepping up to (not past) operated foot (can use scales to check weight you're

2 to 6 weeks Progress more weight onto foot and start ankle movement WBAT

WBAT (weight bear as tolerated = up to full weight) in air-cast boot with crutches, boot inflated

- Boot on for all walking using 2 crutches
- You may be able to manage with 1 crutch indoors (crutch in opposite hand to foot)
- If painful or limping continue with 2 crutches
- Aim for step-through gait – Physiotherapist to review and advise

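### Aim 1 compares instructed with actual weight-bearing in intensity and total time, but no instructed loading time is documented for the boot phase, and no planned item records the instruction each patient received

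*Protocol*

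**What the plan says.** Section 3.0 makes feasibility outcomes the key outcomes. Section 3.1 gives Aim 1, the boot phase ("week 1 to approximately week 6"), two feasibility measures. One of them is "The correlation between instructed amount of weight-bearing and actual weight-bearing, in both intensity and total time". The same section says the device records "peak load, average load, load duration, steps/day", so actual intensity and actual loading time are both measurable.

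The written instruction to patients is the Appendix 1 leaflet.
- **Weeks 0 to 2:** partial weight-bearing, defined as "<50% of your body weight", with no weight-bearing at all also acceptable if painful. The only daily time figure is "aim to keep your leg elevated 23hrs/day".
- **Weeks 2 to 6:** "WBAT (weight bear as tolerated = up to full weight) in air-cast boot with crutches, boot inflated".

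The leaflet opens with "The following is a guide only, please check for any changes or variances as indicated by your" and refers the reader to the surgeon's post-operative plan. Section 2.3 says "Postoperative rehabilitation will be standardised for the initial 12-week rehabilitation period for all included patients", and exclusion 4 in section 2.7.2 removes patients who need non-standard care after surgery. Section 3.2 has the physiotherapist instruct each patient at week 2 and places the start of partial weight-bearing after that visit.

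In Table 1 (section 4.0) the weight-bearing row lists sensor data only. The REDCap forms for weeks 2, 6 and 12 (Appendix 5) hold the visit date, AFORM, EQ-5D 5L, its VAS and the knee-to-wall distance.

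**The concern.** Comparing instructed with actual behaviour needs a value on each side for the same patient and period. The sensor gives one side. The other has to come from a documented instruction or a recorded one.

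For time, the leaflet contains no instruction to compare with. For intensity it contains a default ceiling, but the default can be overridden, is stated in two ways, and is not planned to be captured as given. An SAP can choose a coefficient or a summary. It cannot supply an instruction that was never given, and it cannot recover one that was never collected.

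At stake is one of the two Aim 1 feasibility measures. Half of it may not be producible as named. In the other half, a patient who correctly follows a changed plan would look like a deviator, or a deviator would look compliant, with nothing in the study data to show which.

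**Working it through.** The plan states no figure for this outcome, so there is none to reproduce. The check traces the reference quantity and then shows what its absence does.

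**1. Instructed loading time in the boot phase.**

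| Period | Days | Intensity instruction | Loading-time instruction |
|---|---|---|---|
| Weeks 0–2 | 14 | Below 50% of body weight; none is also acceptable | None. Elevation 23 h/day; essential walking only in the first week, without minutes |
| Weeks 2–6 | 28 | As tolerated, up to full weight | None. Boot and crutches for all walking; seated exercises with the boot off |

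Taking the window as 6 × 7 = 42 days, 28/42 = 67% have no figure that even bounds walking or loading time. In the other 14 days the elevation target leaves 24 − 23 = 1 h/day. That is time with the leg not elevated, so it caps loading time without instructing any.

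**2. Could the elevation figure serve as a reference?** The correlation is r = cov(x, y) / (SD(x) × SD(y)). If x is 1 h/day for every patient, SD(x) = 0 and r is undefined. A numerical check with 12 patients and a constant x returned no value. So on the documented instructions there is no time correlation in either period.

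**3. Intensity reference.** The leaflet gives one ceiling per phase: 50%, then 100%. Within a phase x is again constant and r is undefined. A correlation exists only by pooling phases, where it largely reflects the step from 50 to 100, or by using instructions that differ between patients, which no planned item records.

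**4. Effect of an unrecorded change of plan (illustration).** Assume 12 patients with two phases each, the leaflet ceilings as x, and perfect compliance with what each patient was told. Assume also that k patients were told to stay at 50% in weeks 2 to 6. Of the 24 patient-phases, 12 have x = 50 and y = 50, 12 − k have x = 100 and y = 100, and k have x = 100 and y = 50. For this two-by-two layout:

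r = 12(12 − k) / √[12 × 12 × (12 − k)(12 + k)] = √[(12 − k)/(12 + k)]

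- k = 0: √(12/12) = 1.000
- k = 1: √(11/13) = 0.920
- k = 2: √(10/14) = 0.845
- k = 3: √(9/15) = 0.775
- k = 4: √(8/16) = 0.707

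Compliance is perfect in every row. The fall comes only from using the leaflet in place of the actual instruction.

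**5. The default stated in two places.** Section 3.2 has partial weight-bearing start after the week-2 visit. Appendix 1 has it in weeks 0 to 2, and up to full weight from week 2. An analyst using one text as the reference would score some patients differently from an analyst using the other, in both periods.

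**The case against.** **Only the actual side needs a time.** The closing words of the outcome could qualify actual weight-bearing alone, so that no instructed time is needed. This reading is strained. It would also leave measured loading time set against an instruction that has no time dimension.

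**The leaflet is not the whole instruction.** Physiotherapists instruct patients before discharge (section 2.9), at week 2 (section 3.2) and at fortnightly sessions (Appendix 2), and may give walking times orally. This stands as a limit: the documents show that the written instruction has no time, not that none is ever given. But an oral instruction helps the analysis only if it is recorded.

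**Standardised care and exclusion 4 already deal with variances.** They make variances less likely. They do not remove them, because screening and consent take place before surgery and the leaflet itself allows for changes afterwards. If care were fully uniform, the reference would be constant within each phase and step 3 would apply.

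**REDCap silence is weak evidence.** This is fair taken alone. The dictionary also lacks fields for return to work and analgesics, which Table 1 plans to collect, and Table 1 lists outcomes rather than reference values. Hospital notes or free-text fields might hold the instruction. Still, neither place plans to collect it.

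**The text is incomplete.** The timeline figures are not shown, one walking instruction in Appendix 1 breaks off, and the Table 2 cited in section 3.2 is not in the readable text. The finding is limited to what can be read.

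A reader might go further and infer that no time is instructed at any point after week 2. The documents do not support that: the leaflet has timed stretches, and a timed bike session for weeks 6 to 8. These are exercises with the boot off and do not fill the gap in loading time.

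**Conclusion.** The point holds for the boot phase. The time half of this Aim 1 outcome has no documented reference: none for about 28 of 42 days, and for the other 14 only an elevation target that is not a loading time and does not vary between patients. The intensity half has a default ceiling per phase, but that default is open to change, is stated inconsistently, and is not planned to be recorded as given.

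A reader might infer that a known share of patients will be misclassified. The documents give no frequency of changed plans, so no share can be stated. The correlations in step 4 show direction and possible size under assumed numbers of changed plans and perfect compliance. They are not a forecast. A reader might also infer that intensity cannot be analysed at all. That is too strong: once the instruction is recorded, actual loading can be set against it.

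The protocol attaches no pass or fail threshold to this correlation. The consequence is therefore a key feasibility measure that is partly unproducible and partly open to misreading, not a wrong trial decision. It should be corrected, and the recording has to be in place before patients are instructed.

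**What to change.** 1. In section 3.1, Aim 1, remove total time from the instructed-versus-actual comparison. Report loaded time per day from the sensor descriptively.
2. Add one item to Table 1 and to REDCap, completed before discharge and at each existing physiotherapy visit. It records the weight-bearing instruction given for the coming period and whether it differs from Appendix 1. Name this entry as the reference for the intensity comparison. The same entry would serve the instructed-versus-actual measure under Aim 2.
3. Reconcile section 3.2 and Appendix 1 on weight-bearing in weeks 0 to 6. Which text is right is a clinical decision for the sponsor.

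The cost is protocol wording and one short field. With one entry before discharge and up to 6 sessions, that is at most 7 entries per patient, or 7 × 12 = 84 in all, at contacts that already take place. Apart from whatever the sponsor settles under item 3, care does not change. One limit remains: if every patient receives the same instruction within a phase, a within-phase correlation stays undefined, and the intensity comparison would have to be reported in another form.

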2.4 Sample Size

A formal sample size calculation is not necessary for the purpose of this feasibility study. Based on the nature of this study, we target a sample size of n=12 patients (5).

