5.0 Withdrawal or dropout from study

Reasons for withdrawal or dropout from the study will be recorded by the research team, particularly as this information may be important for future work. Patients who withdraw or drop out of the study will be asked to return the smart devices to the research team, and no further data collection will take place.

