APPENDIX 5 – REDCap Data Dictionary

Confidential SMART Ankle Fracture Feasibility Study
Page 1 of 8

Demographics

Study ID _____

Date subject signed consent _____
(YYYY-MM-DD)

Age (years) _____

Gender Male
 Female

Height (cm) _____

Weight (kilograms) _____

BMI _____

Comments _____

08.06.2022 8:12pm www.projectredcap.org 

Confidential SMART Ankle Fracture Feasibility Study
Page 2 of 8

Injury Details

Date of Injury _____

Cause of Injury Motor Vehicle Accident
 Motorbike Accident
 Bicycle Accident
 Pedestrian Involved in Road Accident
 Hit by Object
 Fall < 2 metres
 Fall > 2 metres
 Sport Related Accident
 Other

Details of cause of injury if 'other' _____

Imaging Reports (XR/CT/MRI) related to Ankle # _____

Other Concurrent Injuries None
 Musculo-skeletal injury
 Organ injury
 Soft Tissue injury
 Traumatic Brain Injury
 Spinal Cord injury
 Other

Details of other injuries (if applicable) _____

Co-morbidities None
 Cardiovascular Disease
 Lung Disease
 Liver Disease
 Kidney Disease
 Cancer within the last 5 years
 Infectious Disease
 Mental Health Disorder
 Other

Details of Comorbidities (if 'other') _____

Charlson Comorbidity Index Score _____

08.06.2022 8:12pm www.projectredcap.org 

Confidential SMART Ankle Fracture Feasibility Study
Page 3 of 8

Surgery and Other Treatments

Surgical Intervention Yes
 No

Surgery Date _____

Surgery Description _____

Other Treatments Physiotherapy
 Occupational Therapy
 Other

Details of Treatments if 'Other' _____

08.06.2022 8:12pm www.projectredcap.org 

Confidential SMART Ankle Fracture Feasibility Study
Page 4 of 8

Week 2 Data

2 weeks post operatively

Date of Week 2 visit _____

AFORM Score _____

EQ 5D 5L _____

EQ 5D 5L VAS _____

Knee to Wall measurement (in mm) _____

08.06.2022 8:12pm www.projectredcap.org 

Week 6 Data

Week 6

Date of Week 6 visit _____

AFORM Score _____

EQ 5D 5L _____

EQ 5D 5L VAS _____

Knee to Wall measurement (in mm) _____

Week 12 Data

12 weeks

Date of 12 Week visit _____

AFORM Score _____

EQ 5D 5L _____

EQ 5D 5L VAS _____

Knee to Wall measurement (in mm) _____

Completion Data

Study Completion Information

Has patient completed study? No Yes

Put a date if patient withdrew study _____

Reason patient withdrew from study Non-compliance Did not wish to continue in study Other

Date of study completion _____

Was all equipment returned to RBWH? Yes No

General Comments

Comments _____

Adverse Event Report

Adverse Event Date _____

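### Patients who leave because of the device are never interviewed: the acceptability interview comes only after week 12 and data collection stops at withdrawal, so interview-based acceptability may be overstated

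*Protocol*

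**What the plan says.** Protocol section 2.1 makes acceptability and feasibility of the Magnes device the study objective. Section 2.4 sets the size: "we target a sample size of n=12 patients (5").

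Section 3.1 lists three patient acceptability measures under both Aim 1 (device in the Aircast boot) and Aim 2 (NUSHU shoe): keeping the device charged, device-related adverse events, and an interview.

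- **Aim 1 interview:** "semi-structured phone interview after Assessment 3 (12 weeks postoperatively) will be conducted and analysed to gain insight in the acceptability". The selection rule follows: "Every second participant will be selected to receive a phone call (participants 2, 4, 6, 8, 10, 12").
- **Aim 2 interview:** the same time point, "semi-structured phone interview after Assessment 3 (12 weeks postoperatively) will be conducted and analysed", with no selection rule.

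Section 5.0 says "Reasons for withdrawal or dropout from the study will be recorded by the research team". It then says that those who withdraw or drop out will be asked to return the devices, "and no further data collection will take place".

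The Completion Data page in Appendix 5 offers these choices: "Reason patient withdrew from study Non-compliance Did not wish to continue in study Other".

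Table 1 in section 4.0 asks about wear time and charging (item 2) and any other problem limiting use of the device (item 3) at 2, 6 and 12 weeks. These questions are not limited to the interviewees. The protocol describes neither an exit interview nor a rule for replacing a selected interviewee who leaves.

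**The concern.** The interview is the only in-depth measure of what patients think of the device. It can be given only to people still in the study after week 12. Someone who finds the device intolerable and leaves in week 4 has ended their data collection eight weeks before the interview is due. If leaving is related to the device, the interviews over-represent those who were content with it.

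The study is meant to inform a larger randomised trial (sections 1 and 2.1). Patients who rejected the device would be among the most informative for that trial, because their reasons bear on its retention and on whether its device data would be complete.

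A second, separate matter is quantity. With 12 patients, interviewing six leaves a fair chance that a problem shared by a minority is not mentioned in any interview.

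**Working it through.** **Plan's own figures.** Section 2.4 gives 12 patients and states "A formal sample size calculation is not necessary for the purpose of this feasibility study", so there is no calculation to reproduce. The even numbers from 1 to 12 number six, as listed.

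**Step 1: who can be interviewed.** Section 3.1 places the interview after week 12. Section 5.0 ends data collection at withdrawal or dropout. Together these give a participant who leaves before week 12 no chance of interview, whether odd- or even-numbered.

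**Step 2: size of the bias.** Let d be the proportion who leave, a_c the acceptance among completers and a_w the acceptance among leavers. Acceptance in all participants is (1 − d)·a_c + d·a_w. Interviews of completers estimate a_c. The overstatement is therefore

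a_c − [(1 − d)·a_c + d·a_w] = d·(a_c − a_w).

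The protocol gives neither d nor the gap, so both are assumed here. In the extreme case, all leavers reject the device and all completers accept it (gap of 100 points):

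| Device-related leavers of 12 | Acceptance, completers | Acceptance, all 12 | Overstatement |
|---|---|---|---|
| 0 | 100% | 100% | 0 points |
| 1 | 100% | 11/12 = 91.7% | 8.3 points |
| 2 | 100% | 10/12 = 83.3% | 16.7 points |
| 3 | 100% | 9/12 = 75.0% | 25.0 points |
| 4 | 100% | 8/12 = 66.7% | 33.3 points |

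With d from 10% to 30% and a gap from 30 to 100 points, the range is 0.10 × 30 = 3 points to 0.30 × 100 = 30 points.

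**Step 3: does the every-second rule add bias?** No. Whether a participant's enrolment number is odd or even has no reason to be related to liking the device, so the expected bias from the rule is zero. What it costs is information. If a problem affects a proportion p of patients, and patients are independent with no dropout, n interviews all miss it with probability (1 − p)^n:

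- p = 20%: 0.8^6 = 26% with six interviews; 0.8^12 = 7% with twelve.
- p = 10%: 0.9^6 = 53% with six; 0.9^12 = 28% with twelve.

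Dropout shrinks the six further unless leavers are replaced. At an assumed 10%, 20% or 30% dropout, the expected number of interviews is 6 × 0.9 = 5.4, 6 × 0.8 = 4.8 or 6 × 0.7 = 4.2. The chance that all six take place is 0.9^6 = 53%, 0.8^6 = 26% or 0.7^6 = 12%.

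**Step 4: would exit interviews for even-numbered leavers be enough?** With k leavers spread at random over 12 numbers, the chance that none is even-numbered is C(12 − k, 6)/C(12, 6):

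- k = 1: 462/924 = 50%
- k = 2: 210/924 = 23%
- k = 3: 84/924 = 9%
- k = 4: 28/924 = 3%

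With one or two leavers, the every-second rule would too often miss them all, so an exit interview has to be offered whatever the number.

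**Step 5: what the other channels capture.** Table 1 items 2 and 3 reach a participant at weeks 2, 6 and 12. Someone who leaves before week 2 is not asked. Someone who leaves between visits is not asked about the problem that arose after the last one. The withdrawal reason is recorded, but a device rejecter could fit any of the three REDCap choices. Free text under Other or General Comments may hold the detail, but nothing requires it.

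**The case against.** The strongest reply is that the protocol does listen to leavers. Section 5.0 commits to recording reasons for withdrawal and dropout because they may matter for later work. Table 1 asks about device problems at each assessment, and charging and device-related adverse events are further acceptability measures. All of this stands. A reader might infer from the interview timing that people who reject the device are never asked about it; the documents do not support that. What they support is narrower: such people are not interviewed, and the coded withdrawal reason cannot identify them.

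Four further inferences are tempting and also go too far.

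- *Stopping the device equals withdrawal.* No section says so. Sections 2.6 and 5.0 make return of the device follow from withdrawal, not the reverse. Table 1 item 2 anticipates poor use within the study, and section 3.1 provides phone collection of outcomes when visits are missed. A dissatisfied patient who stays enrolled can still be interviewed. Non-compliance as a withdrawal reason hints at overlap but sets no rule.
- *Only even-numbered participants are interviewed in the whole study.* The rule stands under Aim 1 alone.
- *Selecting even numbers pushes acceptability upward.* It does not (Step 3).
- *Interviewees who leave are not replaced.* The protocol is silent; it does not rule replacement out.

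It is also fair to say that the interviews are qualitative and that the protocol defines no acceptability proportion. The percentages in Step 2 therefore illustrate direction and possible size; they do not correct a planned estimate. Ending research data collection when a patient truly withdraws consent is ordinary practice and no error.

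**Conclusion.** The concern holds in limited form. As written, the in-depth patient measure of acceptability excludes everyone who leaves before week 12, and no exit interview makes up for it. If any departure is due to the device, interview-based acceptability is likely to be overstated. Under the assumptions shown, the size runs from zero (no device-related departure) to 33 points (4 of 12, all others accepting). The actual value cannot be known, because the protocol gives no dropout rate. The bias belongs to the interview component and not to every acceptability measure. Withdrawal reasons and the Table 1 questions reduce the gap but do not close it.

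The every-second rule is a separate loss of information: a 26% against a 7% chance that the interviews miss a problem affecting one patient in five. That comparison concerns the interviews only, since such a problem might still surface through Table 1. The protocol should be changed; the defect is moderate and cheap to remedy.

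**What to change.** 1. Amend section 5.0 so that every participant who withdraws or stops using the device, whatever their number, is offered a brief exit interview at that point, with consent.
2. In section 3.1, interview all 12 participants and state that this applies to both Aim 1 and Aim 2.
3. Add a device-related reason to the withdrawal field in the REDCap Completion Data page.
4. State that a participant who stops using the device without withdrawing consent stays in follow-up for A-FORM, EQ-5D and adverse events at the standard visits. Appendix 2 describes the 2-, 6- and 12-week visits as standard care, so this adds no visits.

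The cost is about six extra phone calls (12 − 6), a few sentences in sections 3.1 and 5.0, and one form option. If the Aim 2 interview already covers all 12, one call can serve both aims and the extra cost is only a longer call for the six who would not have had the Aim 1 questions.
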